Appendix 3. Planned Laboratory Assays

Table 5. Planned Laboratory Assays

Laboratory Category	Assay Grouping	Assay
Chemistry		Sodium Potassium Chloride Bicarbonate Glucose BUN Creatine Creatinine phosphokinase ALT AST GGT ALP TBL Calcium Magnesium Phosphorous LDH Uric acid Total protein Albumin CRP Total cholesterol HDL cholesterol LDL cholesterol Triglycerides
Hematology		Hemoglobin Hematocrit RBC count Platelet count
	RBC indices	MCV MCH MCHC
	WBC count with differentials	Neutrophils – absolute and percent Lymphocytes – absolute and percent Monocytes – absolute and percent Eosinophils – absolute and percent Basophils – absolute and percent
Urinalysis	Dipstick	pH SG Protein Blood

		Glucose
		Ketones
		Microscopic examination if blood or protein is present
Serum/urine pregnancy tests		Highly sensitive hCG pregnancy test*
Other tests	Immunogenicity	ADA
	PD and biomarker assessments	Serum: soluble LIGHT Serum: Inflammatory proteins** PBMC: Immunophenotyping** Sputum: soluble LIGHT**
	PK assessments	Plasma: AVTX-002

ADA = anti-drug antibody; ALP = alkaline phosphatase; ALT = alanine aminotransferase; AST = aspartate aminotransferase; BUN = blood urea nitrogen; CRP = Creactive protein; GGT = gamma glutamyl transferase; hCG = human chorionic gonadotropin; HDL = high-density lipoprotein; LDH = lactate dehydrogenase; LDL = low-density lipoprotein; LIGHT = Lymphotoxin-like, exhibits Inducible expression, and competes with Herpes Virus Glycoprotein D for Herpesvirus Entry Mediator, a receptor expressed by T lymphocytes; MCH = mean corpuscular hemoglobin; MCHC = mean corpuscular hemoglobin concentration; MCV = mean corpuscular volume; PBMC = peripheral blood mononuclear cells; PD = pharmacodynamic/s; PK = pharmacokinetic/s; RBC = red blood cell; SAP = statistical analysis plan; SG = Specific Gravity; TBL = total bilirubin; WBC = white blood cell

* For women of childbearing potential

** Samples for these analyses are collected as per the Schedule of Assessments ([Table 2](#)); however, these results are reported separately (as applicable), and will not form part of the statistical analysis described in this SAP

Appendix 4. Potentially Clinically Important Criteria

Table 6. Liver Function PCI Criteria

Laboratory Parameter	PCI Criteria
ALT	$> 3 \times \text{ULN}$; $> 5 \times \text{ULN}$; $> 10 \times \text{ULN}$
AST	$> 3 \times \text{ULN}$; $> 5 \times \text{ULN}$; $> 10 \times \text{ULN}$
TBL	$> 1.5 \times \text{ULN}$
ALT and TBL	ALT $> 3 \times \text{ULN}$ and TBL $> 2 \times \text{ULN}$
AST and TBL	AST $> 3 \times \text{ULN}$ and TBL $> 2 \times \text{ULN}$
ALT/AST and TBL and ALP	ALT/AST $> 3 \times \text{ULN}$ and TBL $> 2 \times \text{ULN}$ and ALP $< 2 \times \text{ULN}$ (Hy's Law Criteria)

ALP = alkaline phosphatase; ALT = alanine aminotransferase; AST = aspartate aminotransferase;
PCI = potentially clinically important; TBL = total bilirubin; ULN = upper limit of normal

Table 7. Safety Laboratory PCI Criteria

Laboratory Parameter	SI Unit	Lower Limit	Upper Limit
Creatinine	$\mu\text{mol/L}$		> 150
Sodium	mmol/L	≤ 130	> 150
Potassium	mmol/L	< 3.0	> 5.5
TBL	$\mu\text{mol/L}$		$> 1.5 \times \text{ULN}$
ALT	U/L		$> 3 \times \text{ULN}$
AST	U/L		$> 3 \times \text{ULN}$
Hemoglobin	g/L	$< 0.8 \times \text{LLN}$ and $> 20\%$ decrease from baseline	$> 1.3 \times \text{ULN}$ and $> 30\%$ increase from baseline
Leukocytes	$\times 10^9/\text{L}$	≤ 2.8	≥ 16.0
Lymphocytes	$\times 10^9/\text{L}$	< 0.5	> 20
Neutrophils	$\times 10^9/\text{L}$	< 1.0	
Platelets	$\times 10^9/\text{L}$	≤ 75	≥ 500

ALT = alanine aminotransferase; AST = aspartate aminotransferase; LLN = lower limit of normal;
PCI = potentially clinically important; TBL = total bilirubin; ULN = upper limit of normal

Table 8. Vital Signs PCI Criteria

Vital Signs Parameter	PCI Criteria
SBP	$\leq 90 \text{ mmHg}$ and decrease of $\geq 20 \text{ mmHg}$ from baseline $\geq 180 \text{ mmHg}$ and increase of $\geq 25 \text{ mmHg}$ from baseline
DBP	$\leq 50 \text{ mmHg}$ and decrease of $\geq 15 \text{ mmHg}$ from baseline $\geq 105 \text{ mmHg}$ and increase of $\geq 15 \text{ mmHg}$ from baseline
Pulse rate	$\leq 40 \text{ bpm}$ $\geq 100 \text{ bpm}$

DBP = diastolic blood pressure; PCI = potentially clinically important; SBP = systolic blood pressure

Appendix 5. Laboratory CTCAE Criteria

Table 9. Laboratory CTCAE Grade Version 5.0 Criteria

Lab Parameter	SI Unit	CTCAE Grade v5.0				
		Grade 0	Grade 1	Grade 2	Grade 3	Grade 4
Hemoglobin decreased (Anemia)	g/L	≥ LLN	100 – < LLN	80 – < 100	< 80	
Hemoglobin increased	g/L	≤ ULN	> ULN – 2 × ULN	> 2 × ULN – 4 × ULN	> 4 × ULN	
Hypoglycemia (Glucose decreased)	mmol/L	≥ LLN	3.0525 – < LLN	2.22 – < 3.0525	1.665 – < 2.22	< 1.665
Glucose (hyperglycemia)	mmol/L	LLN – ULN	> ULN – 8.88	> 8.88 – 13.875	> 13.875 – 27.75	> 27.75
Albumin	g/L	≥ LLN	< LLN – 30	< 30 – 20	< 20	Life-threatening consequences; urgent intervention indicated*
ALP		≤ ULN	> ULN – 2.5 × ULN	> 2.5 – 5.0 × ULN	> 5.0 – 20.0 × ULN	> 20.0 × ULN
ALT increased	U/L	≤ ULN	> ULN – 3 × ULN	> 3 × ULN – 5 × ULN	> 5 × ULN – 20 × ULN	> 20 × ULN
AST increased	U/L	≤ ULN	> ULN – 3 × ULN	> 3 × ULN – 5 × ULN	> 5 × ULN – 20 × ULN	> 20 × ULN
Blood bilirubin increased	umol/L	≤ ULN	> ULN – 1.5 × ULN	> 1.5 × ULN – 3 × ULN	> 3 × ULN – 10 × ULN	> 10 × ULN
Creatinine increased	umol/L	≤ ULN	> ULN – 1.5 × ULN	> 1.5 × ULN – 3 × ULN	> 3 × ULN – 6 × ULN	> 6 × ULN
Calcium (hypocalcemia)	mmol/L	LLN – ULN	< LLN – 2.0	< 2.0 – 1.8	< 1.8 – 1.5	< 1.5
Calcium (hypercalcemia)	mg/dL	LLN – ULN	> ULN – 2.9	> 2.9 – 3.1	> 3.1 – 3.4	> 3.4
Eosinophils increased	× 10 ⁹ /L	≤ ULN	> ULN and > Baseline			
Lymphocyte count decreased	× 10 ⁹ /L	≥ LLN	0.8 – < LLN	0.5 – < 0.8	0.2 – < 0.5	< 0.2
Lymphocyte count increased	× 10 ⁹ /L	≤ 4		> 4 – 20	> 20	
Neutrophil count decreased	× 10 ⁹ /L	≥ LLN	1.5 – < LLN	1 – < 1.5	0.5 – < 1.0	< 0.5
Platelet count decreased	× 10 ⁹ /L	≥ LLN	75 – < LLN	50 – < 75	25 – < 50	< 25

Lab Parameter	SI Unit	CTCAE Grade v5.0				
		Grade 0	Grade 1	Grade 2	Grade 3	Grade 4
WBC count decreased	$\times 10^9/\text{L}$	$\geq \text{LLN}$	$3 - < \text{LLN}$	$2 - < 3$	$1 - < 2$	< 1
WBC count increased (leukocytosis)	$\times 10^9/\text{L}$	≤ 10			> 10	
Hyperkalemia (Potassium increased)	mmol/L	$\leq \text{ULN}$	$> \text{ULN} - 5.5$	$> 5.5 - 6.0$	$> 6.0 - 7.0$	> 7.0
Hypokalemia (Potassium decreased)	mmol/L	$\geq \text{LLN}$	$3.0 - < \text{LLN}$	Symptomatic with $3.0 - < \text{LLN}^{**}$	$2.5 - < 3.0$	< 2.5
Hypernatremia (Sodium increased)	mmol/L	$\leq \text{ULN}$	$> \text{ULN} - 150$	$> 150 - 155$	$> 155 - 160$	> 160
Hyponatremia (Sodium decreased)	mmol/L	$\geq \text{LLN}$	$130 - < \text{LLN}$	$125 - < 130$	$120 - < 125$	< 120
Bicarbonate decreased		$\geq \text{LLN}$	$< \text{LLN}$			
CPK increased		$\leq \text{ULN}$	$> \text{ULN} - 2.5 \times \text{ULN}$	$> 2.5 \times \text{ULN} - 5 \times \text{ULN}$	$> 5 \times \text{ULN} - 10 \times \text{ULN}$	$> 10 \times \text{ULN}$
GGT increased		$\leq \text{ULN}$ if baseline was normal; $\leq 2.0 \times \text{ULN}$ if baseline was abnormal	$> \text{ULN} - 2.5 \times \text{ULN}$ if baseline was normal; $2.0 - 2.5 \times \text{ULN}$ if baseline was abnormal	$> 2.5 - 5.0 \times \text{ULN}$ if baseline was normal; $2.0 - 5.0 \times \text{ULN}$ if baseline was abnormal	$> 5 - 20.0 \times \text{ULN}$ if baseline was normal; $> 5 - 20.0 \times \text{ULN}$ if baseline was abnormal	$> 20.0 \times \text{ULN}$ if baseline was normal; $> 20.0 \times \text{ULN}$ if baseline was abnormal
Hypermagnesemia (magnesium increased)	mmol/L	$\leq \text{ULN}$	$> \text{ULN} - 1.23$		$> 1.23 - 3.30$	> 3.30
Hypomagnesemia (magnesium decreased)	mmol/L	$\geq \text{LLN}$	$< \text{LLN} - 0.5$	$< 0.5 - 0.4$	$< 0.4 - 0.3$	< 0.3
LDH increased		$\leq \text{ULN}$	$> \text{ULN}$			
Total cholesterol high	mmol/L	$\leq \text{ULN}$	$> \text{ULN} - 7.75$	$> 7.75 - 10.34$	$> 10.34 - 12.92$	> 12.92
Hypertriglyceridemia (triglycerides increased)	mmol/L	≤ 1.71	$1.71 - 3.42$	$> 3.42 - 5.7$	$> 5.7 - 11.4$	> 11.4

ALP = alkaline phosphatase; ALT = alanine aminotransferase; AST = aspartate aminotransferase;

CTCAE = common terminology criteria for adverse events; CPK = creatinine phosphokinase; GGT = gamma glutamyl transferase; LDH = lactate dehydrogenase; LLN = lower limit of normal; ULN = upper limit of normal; WBC = white blood cell

* Any albumin $< 20 \text{ g/L}$ will be categorized as Grade 3

** Any potassium $3.0 - < \text{LLN}$ will be categorized as Grade 1

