10.7.2 Clinical Laboratory Values

Subject listings, using the SAS, will be provided for all clinical laboratory tests, ie, hematology, clinical chemistry, urinalysis, and pregnancy tests.

Observed values of hematology and clinical chemistry parameters, and continuous urinalysis parameters (SG, pH) at selected time points, and change from baseline in these parameters at each post-baseline time point, will be summarized descriptively by treatment group. The overall worst value post-baseline (which includes results from unscheduled visits) will also be included in the summaries. Table 10 provides the directionality of the worst values for each laboratory parameter.

Shift tables for hematology and clinical chemistry laboratory parameters, using laboratory CTCAE version 5.0 grading (see Table 9) showing changes from baseline to post-baseline values will be summarized using counts and percentages. For a specific laboratory parameter, subjects with both baseline and a post-baseline value will be included for shift summaries. For computing percentages, the denominator will be the total number of subjects with non-missing baseline and post-baseline values for the respective post-baseline visit point and treatment group.

The number and percentage of subjects meeting criteria for abnormal LFTs (see [Table 6](#)) will be summarized by treatment group and time point (including results from unscheduled visits). For computing percentages, the denominator will be the number of subjects with a post-baseline value for the specific laboratory parameter and the respective time point. Only subjects with newly occurring values (at least one post-baseline measurement meeting the criterion but not meeting the criterion at baseline) will be counted.

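### Two rows of SAP Table 9 (hypercalcemia and abnormal-baseline GGT) give wrong or non-unique CTCAE grades as printed; the leukocytosis row needs only a check

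*SAP*

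**What the plan says.** SAP section 10.7.2 specifies hematology and chemistry shift tables "using laboratory CTCAE version 5.0 grading (see Table 9) showing changes from baseline to post-baseline values". The same section refers to toxicity grading being derived from the numeric result, so the grades come from a program applying Table 9.

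Three rows of Table 9 matter here.

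- **Calcium.** The unit column is headed SI Unit. The row "Calcium (hypocalcemia" is in mmol/L, with cut-offs 2.0, 1.8 and 1.5. The row "Calcium (hypercalcemia" is in mg/dL, with cut-offs 2.9, 3.1 and 3.4. Its Grade 0 is the normal range and its Grade 4 is anything above 3.4.
- **GGT.** The row "GGT increased" has separate limits for normal and abnormal baseline. For an abnormal baseline, Grade 0 is ≤2.0, Grade 1 is 2.0-2.5, Grade 2 is 2.0-5.0, Grade 3 is >5-20 and Grade 4 is >20, all × ULN.
- **WBC.** The row "WBC count increased (leukocytosis" has Grade 0 at ≤10 and Grade 3 at >10 × 10⁹/L. The Grade 1 and 2 cells are empty. Table 7 (Appendix 4) sets the upper PCI limit for leukocytes at ≥16.0 × 10⁹/L.

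The two footnotes to Table 9 resolve ambiguous albumin and potassium grades. Neither covers calcium, GGT or WBC.

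**The concern.** A shift table needs each value to fall in exactly one grade, at baseline and at each later visit. The hypercalcemia row has a unit that does not fit its own numbers, and the abnormal-baseline GGT row has overlapping intervals. A programmer following the text would have to depart from it for calcium and make an unwritten choice for GGT.

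At stake is the graded laboratory safety output. With about 40 subjects per arm, a few spurious high-grade shifts, or GGT grades that depend on the order of the program's conditions, would change how those tables read.

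**Working it through.** **1. Calcium**

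Inputs: the Table 9 cut-offs, and the conversion 1 mmol/L = 4.0078 mg/dL. The conversion is not in the documents; it follows from calcium's atomic mass of 40.078.

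- Hypercalcemia cut-offs as printed, in mmol/L: 2.9/4.0078 = 0.724; 3.1/4.0078 = 0.773; 3.4/4.0078 = 0.848. All lie below the table's own Grade 4 hypocalcemia limit of 1.5 mmol/L.
- Grade 1 hypocalcemia runs from below the LLN down to 2.0 mmol/L, so the LLN must exceed 2.0 × 4.0078 = 8.02 mg/dL. The ULN is higher still.
- Grade 1 hypercalcemia, above the ULN and up to 2.9 mg/dL, is therefore empty.
- Every normal calcium exceeds 8.02 mg/dL, hence exceeds 3.4 mg/dL, and so meets both Grade 0 and Grade 4. No assumed ULN is needed.
- Read as mmol/L, the cut-offs equal 11.62, 12.42 and 13.63 mg/dL. They lie above the hypocalcemia cut-offs of 8.02, 7.21 and 6.01 mg/dL, and the row is ordered and usable.

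Illustration with an assumed ULN of 10.2 to 10.5 mg/dL (the grades are the same at both ends):

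| Calcium, mg/dL | mmol/L | Grade, unit as printed | Grade, unit mmol/L |
|---|---|---|---|
| 9.5 | 2.37 | 0 and 4 | 0 |
| 10.8 | 2.69 | 4 | 1 |
| 12.0 | 2.99 | 4 | 2 |
| 12.8 | 3.19 | 4 | 3 |
| 14.0 | 3.49 | 4 | 4 |

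**2. GGT**

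Each value is assigned to every Table 9 interval that it satisfies:

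| GGT, × ULN | Normal baseline | Abnormal baseline |
|---|---|---|
| 1.5 | 1 | 0 |
| 2.0 | 1 | 0, 1 and 2 |
| 2.2 | 1 | 1 and 2 |
| 2.5 | 1 | 1 and 2 |
| 2.6 | 2 | 2 |
| 5.0 | 2 | 2 |
| 5.1 | 3 | 3 |

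The normal-baseline limits do not overlap, because Grade 2 starts above 2.5. If the lower bounds in the abnormal-baseline cells are read as exclusive, 2.0 becomes Grade 0 only, but everything above 2.0 up to 2.5 still has two grades. The branch can be reached: no entry criterion limits GGT, and exclusion criterion 12 sets the transaminase exclusion at above 5 × ULN. A baseline of, say, 2.2 × ULN would itself have two grades, so its starting row in the shift table would be undefined.

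**3. WBC (comparison only)**

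A WBC of 10.1, 12 or 15.9 × 10⁹/L is Grade 3 but not PCI; 16 is both. With Grades 1 and 2 empty, the only upward shift possible is from Grade 0 to Grade 3. Table 9 also grades lymphocytes of >4-20 as Grade 2. A lymphocyte count of 12 is therefore Grade 2, while the total WBC containing it is Grade 3.

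**The case against.** The calcium entry can be called a label slip that would cause no harm. The heading and the neighboring row both point to mmol/L, and SI results compared with the printed numbers grade sensibly. Grade 4 for nearly every subject would also be noticed at once. That makes an unnoticed error unlikely, and it is one reason to rate the point as minor. It does not make the written rule correct, because the sensible result comes from ignoring the printed unit.

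The GGT overlap is narrow. It affects only subjects with an abnormal baseline and values from 2.0 to 2.5 × ULN. That limits its size, but nothing in the SAP says which grade applies.

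On WBC, a reader might infer that the Grade 3 limit of >10 and the PCI limit of ≥16.0 cannot both be right, or that the row should be changed to agree with Table 7. The documents do not support this:

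- PCI criteria and CTCAE grades are separate outputs in SAP 10.7.2 and differ elsewhere. A WBC of 2.9 is Grade 2 low but not PCI, since the PCI limit is ≤2.8. A hemoglobin above 1.3 × ULN with a rise of more than 30% is PCI, but only Grade 1 if it is no higher than 2 × ULN.
- Empty cells are not a sign of error. Lymphocyte increase has no Grade 1 and hypermagnesemia has no Grade 2.
- Protocol section 11.2 describes Grade 3 as severe or medically significant when an investigator grades an adverse event, not when a laboratory value is binned.

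The lymphocyte comparison justifies a check of the row, but it does not show which number is wrong.

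**Conclusion.** Two rows of Table 9 are wrong as written. The hypercalcemia unit makes the row unusable if followed literally, and this rests only on the table's own cut-offs and the calcium conversion. The abnormal-baseline GGT intervals give two grades from above 2.0 to 2.5 × ULN and three at exactly 2.0; this needs no outside figure. The leukocytosis row is a query, because the CTCAE v5.0 text is not among the documents.

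A reader might also infer that the trial's safety conclusions are at risk. The documents do not bear that out. The shift tables are descriptive, and no formal inferential safety analysis is planned. Listings, observed and change-from-baseline summaries, worst values, and the liver-function and PCI tables do not depend on these rows. Clinically relevant laboratory changes are reported as adverse events and graded under protocol section 11.2, not from Table 9. Efficacy is untouched. Severity: minor.

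**What to change.** - **Hypercalcemia:** change the unit to mmol/L, and convert any result received in mg/dL before grading.
- **GGT, abnormal baseline:** make the intervals mutually exclusive: Grade 0 ≤2.0, Grade 1 >2.0-2.5, Grade 2 >2.5-5.0 × ULN. This matches the start of Grade 2 in the normal-baseline entry. Moving only the start of Grade 2 would leave exactly 2.0 × ULN in both Grade 0 and Grade 1. Check the whole row against the CTCAE v5.0 text before fixing it.
- **Leukocytosis:** verify the row against CTCAE v5.0 and correct it only if it departs from that text. Do not fit it to Table 7.

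The cost is a correction to a few cells of one appendix table, ideally before the shift tables are produced. If they are already programmed, the grading step and those tables must be rerun. No new data are needed and no other analysis changes.

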Appendix 6. Directionality of Worst Laboratory Parameters

Table 10. Directionality of Worst Laboratory Parameters

Laboratory Parameter	Worst Value
Hematology:	
Hemoglobin	Both highest and lowest value
Hematocrit	Both highest and lowest value
RBC count	Both highest and lowest value
Platelet count	Lowest value
MCV	Both highest and lowest value
MCH	Both highest and lowest value
MCHC	Both highest and lowest value
WBC count	Both highest and lowest value
Neutrophils	Lowest value
Lymphocytes	Both highest and lowest value
Monocytes	Both highest and lowest value
Eosinophils	Both highest and lowest value
Basophils	Both highest and lowest value
Chemistry:	
Sodium	Both highest and lowest value
Potassium	Both highest and lowest value
Chloride	Both highest and lowest value
Bicarbonate	Both highest and lowest value
Glucose	Both highest and lowest value
BUN	Highest value
Creatine	Highest value
Creatinine phosphokinase	Highest value
ALT	Highest value
AST	Highest value
GGT	Highest value
ALP	Highest value
TBL	Highest value
Calcium	Both highest and lowest value
Magnesium	Both highest and lowest value
Phosphorous	Both highest and lowest value
LDH	Highest value
Uric acid	Highest value
Total protein	Both highest and lowest value
Albumin	Lowest value
CRP	Highest value
Total cholesterol	Highest value
HDL cholesterol	Highest value
LDL cholesterol	Highest value
Triglycerides	Highest value

ALP = alkaline phosphatase; ALT = alanine aminotransferase; AST = aspartate aminotransferase; BUN = blood urea nitrogen; CRP = Creactive protein; GGT = gamma glutamyl transferase; HDL = high-density lipoprotein; LDH = lactate dehydrogenase; LDL = low-density lipoprotein; MCH = mean corpuscular hemoglobin; MCHC = mean corpuscular hemoglobin concentration; MCV = mean corpuscular volume; RBC = red blood cell; TBL = total bilirubin; WBC = white blood cell
